Early detection is critical for mitigating PAD progression. Ankle-brachial index (ABI) testing is recommended by the US Preventative Services Task Force as an affordable and effective screening tool for evaluating PAD risk[3]. ABI testing is especially useful in primary care settings allowing for earlier diagnosis and treatment. Several ABI methods are used; classically this test uses a device for measuring blood pressure with an inflatable cuff, and blood pressure measurements are taken at the upper arm and the ankle; healthcare providers have used a doppler probe to detect audible systolic pressure signals within the arteries - Doppler ABI. Barriers to implementation include; time required to conduct tests, training and required technical skills. Hence, Doppler-based ABI in primary care has been limited. Recently designed oscillometric (manual or digital with automatic electronic calculation of blood pressure) and photoplethysmographic devices are now available. However current guidelines do not endorse the use of these newer devices but recommend the hand-held doppler technique[4].

Digital ABI is noninvasive, automated ABI using pulsatile blood volume changes - plethysmography, irrespective of vessel compressibility. The QuantaFlo™ (Semler Scientific, Inc.) is an innovative, 510K FDA approved device that provides bilateral, non-invasive physiologic studies of upper and lower extremity arteries using volume plethysmography of the posterior tibial and anterior tibial/dorsalis pedis arterial distributions. QuantaFlo™ uses an optical sensor attached onto a digit in the hand and feet to assess extremity blood volume. It then displays a signal, directly related to blood volume, on a Volume Plethysmography Chart used to calculate PAD probability. This test is easy to use and portable, delivering fast, accurate results in ~5 minutes; an attractive option in primary care settings. While maintaining accuracy, results comparing digital methods to Doppler show concordance above 90%. The American Medical Association (AMA) concluded, "Evaluation of the digits in both legs with volume plethysmography is appropriate for this code provided that an ankle/brachial index (ABI) be performed." QuantaFlo™ meets both of these standards.

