ABI ≤ 0.9 has been used as the criterion for diagnosing PAD based on ACC/AHA guidelines for the management of patients with PAD [3]; the cutoff value of ABPI ≤ 0.9 it has been reported that the sensitivity of diagnosing PAD was 83% to 85% and a specificity of 95% to 100% [5]. ABI has been validated against lower extremity contrast angiography obtaining high sensitivity (85%–95%) and specificity (90%–100%), for diagnosing PAD [6, 7]. Many studies have reported more than 95% of sensitivity and specificity of colour duplex ultrasound scan in detecting a significant stenosis of the arteries [8, 9].

Please save frequently

b) Describe any animal experimentation and findings leading to the formulation of the study, if there is no supporting human data.

Protocol Title: Sensitivity and specificity of digital ankle brachial index (ABI) as a screening tool in detecting peripheral arterial disease: A single center, prospective clinical trial

N/A

2. Purpose of the study

a) Provide a brief lay summary of the project in <200 words. The lay summary should be readily understandable to the general public.

QuantaFlo™ (Semler Scientific, Inc.) is a novel, noninvasive, 510K FDA approved digital device that is used as a screening tool to measure ABI of patients at risk of PAD. This single center prospective clinical trial will evaluate the sensitivity and specificity of digital ABI in detecting PAD using color Doppler ultrasound and 'gold standard' angiography as reference. Specifically in participant undergoing dialysis and who cannot undergo ABI using pressure cuffs dialysis grafts/ fistulae in the arms, we will evaluate the value of digital ABI in detecting PAD.

Page numbers from a sponsor's protocol/grant may be referenced in 2b and 2c.

b) List your research objectives (specific aims & hypotheses of the study).

Primary aim:

To evaluate the sensitivity and specificity of digital ABI in diagnosing PAD using color Doppler ultrasound and 'gold standard' angiography as reference.

Secondary aim:

- To correlate the digital ABI index with symptoms of PAD.
- To evaluate the value of digital ABI in detecting PAD in patients on dialysis in whom the presence of dialysis grafts/ fistulae in the arms would have prohibited the use of ABI using pressure cuffs.

Please save frequently

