3. Screening questionnaire: On registration at these respective clinics, all patients in the clinic will be given the screening questionnaire by the front desk. Patient will fill out the questionnaire, saying YES or NO. If ANY of the questions is a YES - this is an indication for doing a screening digital ABI.
The screening questionnaire is considered part of clinical care, and would occur regardless of this research study.
4. If ANY of the questions is a YES - this is an indication for doing a screening digital ABI. This patient will then be approached by the Research Coordinator and asked if they want to participate. The Research Coordinator will then consent the patient for the study.
5. After consent, an EPIC order will be placed for the ABI. The medical assistant / nurse/ front desk will speak to the study coordinator to put an order for a digital ABI in EPIC. Along with the order, the answers from the screening questionnaire will be entered into EPIC via a flowsheet that has been created. The screening questionnaire will be uploaded in EPIC regardless of this research study.

6. Perform Digital ABI:

Performing ABI is within the normal duties of any nurse/ medical assistant

- Will be performed by the nurse/medical assistant/ research coordinator with training to perform this test
- The participant will be placed in the supine position, with the arms and legs at the same level as the heart, for a minimum of 5 minutes before measurement. Foot warmers will be placed during this time on the patients feet with foot liners. The foot warmers are like a heating pad for feet.
- The optical sensor (similar to a pulse oximeter) will be placed sequentially in the fingers of the hands and feet: Right and left hand fingers and then right and left feet toes.
- Usually each digit takes about 15 seconds to obtain a waveform
- At the end of 60 seconds, an automated digital ABI will be generated.

IF the data produced seem unreliable, sometimes indicated by the device we will ask the

Protocol Title: Sensitivity and specificity of digital ankle brachial index (ABI) as a screening tool in detecting peripheral arterial disease: A single center, prospective clinical trial

participant to do exercise 25-40 heel lifts (until they can feel it in their calf muscle). and then the test with the pulse Oximeter will be repeated.

6. Interpreting ABI: Interventional Radiology physician will pick up these studies from EPIC at the end of the day and put in a formal report in EPIC.

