
7. Clinical course: If based on Screening questionnaire and digital ABI,
I. Participant is diagnosed with PAD- the referring physician and participant will receive a phone call about the same. He/ she will then be advised any further testing/ referral to IR clinic.
II. There is no evidence of PAD- no further action will be taken. The participant will be informed of the same.

8. The data of all patients who have answered the questionnaire will be accessed. This includes those patients who are screened but do not meet the criteria to undergo digital ABI. Those who were screened, do meet the criteria to undergo the digital ABI but choose not to will be asked if their data can still be used for this research study (and will be asked to sign a separate consent document).

c) If the proposed study is a clinical trial where a drug, vaccine, device or other treatment is compared to a placebo group or comparison treatment group, what are the guidelines or endpoints by which early decisions regarding efficacy or lack of efficacy can be made? For example, it may be reasonable to stop enrollment on a study when efficacy has already been clearly demonstrated, to avoid unnecessary enrollments of additional subjects. Alternatively, it may be reasonable to stop enrollment when it is clear that efficacy will never be demonstrated, given the statistical power of the study as designed. Describe the guidelines that are in place to assist in making these determinations, if relevant to the proposed study.

N/A

d) Describe how data analysis will be performed (statistical tests, methods of evaluating data) and indicate the smallest group/unit for which separate reporting will occur. For studies involving a questionnaire, if data and reliability information are available, please describe or provide references. For full board, unfunded studies describe sample size determination and power analysis. If none, please justify.

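### Step 7 II gives the referring physician no active notice when a participant with a leg or foot symptom has a negative digital ABI

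*Combined protocol and SAP*

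**What the plan says.** The combined protocol and SAP, section 3b step 7, opens with "If based on Screening questionnaire and digital ABI" and then sets out two branches. In branch I (PAD diagnosed), "the referring physician and participant will receive a phone call about the same", and further testing or referral to the IR clinic is advised. Branch II reads: "There is no evidence of PAD- no further action will be taken. The participant will be informed of the same". It mentions neither a call to the physician nor an exception for any questionnaire answer.

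Other sections that bear on this:

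- **8h and 3b steps 3 and 4.** A single YES among 11 questions is enough for entry. Four of the questions concern the legs or feet: rest pain, walking discomfort relieved by rest, pale or discoloured toes or feet, and a foot infection, wound or ulcer.
- **3b step 5.** "Along with the order, the answers from the screening questionnaire will be entered into EPIC via a flowsheet".
- **3b, interpretation step.** "Interventional Radiology physician will pick up these studies from EPIC at the end of the day and put in a formal report in EPIC".
- **3f.** Traditional ABI or Doppler ultrasound is the hospital's work-up for patients with signs and symptoms of PAD.
- **2b, primary aim.** "To evaluate the sensitivity and specificity of digital ABI in diagnosing PAD".
- **1a.** For ABI at a cutoff of 0.9, "it has been reported that the sensitivity of diagnosing PAD was 83% to 85% and a specificity of 95% to 100" per cent. Against angiography, the cited ranges are 85% to 95% for sensitivity and 90% to 100% for specificity. The section also says that current guidelines favour the hand-held Doppler technique and do not endorse the newer devices.

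**The concern.** A participant may enter because of rest pain or a foot ulcer, have a normal device result, and leave with the study's conclusion that PAD was not found. The device's sensitivity is the quantity under study, so it cannot be relied on when results are given out. Outside the study, the same complaint would lead to traditional ABI or Doppler ultrasound under 3f. Branch II does not point the participant or the physician back to that route. What is at stake is false reassurance, and possibly a delayed work-up, in the participants most likely to have disease. Sample size, power and the planned analysis are not affected.

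**Working it through.** **Step 1. Does the questionnaire keep symptomatic participants out of branch II?** Step 7 names both the questionnaire and the digital ABI but does not say how they combine. Entry requires at least one YES, so every participant tested has a positive questionnaire. A YES as such therefore cannot separate the branches. Only a rule about particular items could, and none is written.

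**Step 2. Who is told, and when?** Branch I has a phone call. Branch II informs the participant only. The physician can find the questionnaire answers and the formal report in EPIC, but that report is filed at the end of the day, whereas 8k puts the device result at around 5 minutes. It may therefore reach the chart after the visit is over. The gap is one of active notice, not of access.

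**Step 3. How much PAD could remain after a negative result?** The plan states no figure, so there is none to reproduce. With prevalence p, sensitivity Se and specificity Sp,

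P(PAD | negative) = p(1 − Se) / [p(1 − Se) + (1 − p)Sp].

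Inputs:

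- Se and Sp: the most and least favourable pairings within the ranges in 1a, namely 95% with 100%, and 83% with 95%. These describe ABI in general, not this device.
- Low prevalence: continuing review item 16 reports 8 + 2 = 10 confirmed among 238 usable subjects, and 10/238 = 4.2%. This is a floor, because step 7 sends negatives to no reference test. The predictive values printed beside these counts do not follow from them (8/10 = 80%, printed as 67%), so 4.2% is rough.
- Higher prevalence: the documents give none for symptomatic participants. The values 20% to 50% are an assumption.

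Worked example at p = 0.042, Se = 0.83, Sp = 0.95: 0.042 × 0.17 = 0.00714; 0.958 × 0.95 = 0.9101; 0.00714 / 0.91724 = 0.8%.

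| Prevalence | Se 95%, Sp 100% | Se 83%, Sp 95% |
|---|---|---|
| 4.2% | 0.2% | 0.8% |
| 10% | 0.5% | 2.0% |
| 20% (assumed) | 1.2% | 4.3% |
| 30% (assumed) | 2.1% | 7.1% |
| 50% (assumed) | 4.8% | 15.2% |

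If the device's sensitivity were only 70% (a further assumption, with Sp 95%), the figures would be 1.4% at 4.2% prevalence, 7.3% at 20% and 24.0% at 50%.

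The residual risk is therefore small in the mixed screened group and becomes material only where prevalence is higher, as it may be among participants with leg or foot symptoms.

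**The case against.** The strongest reply has four parts.

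1. **Step 7 already counts the questionnaire**, so a participant with rest pain need not land in branch II. That is possible, but it depends on a rule that is not written (step 1 of the working).
2. **The physician is not cut off.** Symptom and result sit in one chart, clinicians remain free to test, and nothing withdraws the 3f standard of care. This stands, and it is why the point is minor.
3. **The device agrees well with Doppler**: 1a says "results comparing digital methods to Doppler show concordance above 90" per cent. Concordance is not sensitivity, however. At 4.2% prevalence, a test that was always negative would agree with the truth in 100% − 4.2% = 95.8% of people.
4. **Step 7 is a procedural summary, not a script**, and the consent forms were not available for this review. A caution may already be given. This also stands.

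A reader might infer three stronger things that the documents do not support:

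- *That the message overstates the result for everyone who screens negative.* Finding no evidence of PAD is not the same as ruling it out, the words actually used are not given, and the residual risk in the mixed group is under 1% at 4.2% prevalence.
- *That 5% to 17% of negatives have PAD.* Those figures are 1 − Se (1 − 0.95 and 1 − 0.83), the share of people with PAD who test negative. What a negative result leaves open is the smaller quantity in the table for the mixed group, and it depends on prevalence.
- *That 194 of 238 (238 − 44; 81.5%) measures the problem.* That is everyone not device-positive, including people with risk factors only and possibly calcified results above 1.4, whose branch is not stated. The number with a leg or foot symptom could be anywhere from 0 to 194.

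**Conclusion.** The point holds for participants who answered YES to a leg or foot item and have a negative digital ABI. For them, branch II as written provides no active physician notice and no caution, although site practice for such patients is further testing and the device's sensitivity is the study question. It is minor: a cheap improvement in patient safety, with no loss of care shown and no count of missed cases possible. The residual risk is about 0.2% to 0.8% at 4.2% prevalence, and about 1% to 15% at 20% to 50%. These figures assume that the ABI accuracy in 1a carries over to this device. The upper range also assumes a prevalence that the documents do not give.

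**What to change.** Add to 3b step 7 II: for a participant with a YES to any of the four leg or foot items in 8h and a negative digital ABI, the referring physician is notified of both the symptom and the negative screen, so that the evaluation in 3f can be considered at that physician's judgement; the participant is told that a negative screen does not rule out PAD. This also settles how questionnaire and device combine for the group where it matters most.

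The cost is a sentence or two in a protocol already being revised (continuing review items 20, 23 and 24), one notice per symptomatic screen-negative, and some extra standard-care tests. Those tests would come from a group selected by symptoms. If their results enter the sensitivity and specificity analysis, they should be labelled as such and not treated as a representative sample of negatives.

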f) Does the study include an investigator's brochure (IB)?

If yes, what is the current version date?

(If study has multiple IBs, attach current versions in Attachments section (#16))

Protocol Title: Sensitivity and specificity of digital ankle brachial index (ABI) as a screening tool in detecting peripheral arterial disease: A single center, prospective clinical trial

16. Provide a summary of any recent findings, literature, or other relevant information (especially pertaining to risks), if applicable.

Of the 238 subjects with usable data, QuantaFlo detected positive results for Peripheral Artery Disease in 44 subjects: 10 with severe, 15 with moderate, and 19 with mild disease. Of the 10 designated severe by QuantaFlo, 8 were confirmed upon follow-up exams and imaging (positive predictive value of 67%). Of those 34 designated mild or moderate by QuantaFlo, 2 were confirmed upon follow-up exams and imaging (positive predictive value of 14%).

17. Have there been any significant amendments or revisions to the protocol during the past approval period? (Significant amendments include changes in study design or risk level including those that resulted in a change in consent).

N

If yes, please briefly summarize the changes:

18. Y The consent materials attached to this eIRB application (including consent documents, assent documents, recruitment statements or other materials used to obtain consent) are the versions being used in the conduct of this study and all enrolled subjects have signed consent forms on file, if required. (If the requirement to obtain consent was waived or if no participants have enrolled since last continuing review, check N/A).

NOTE: The IRB routinely monitors consent document usage and may request copies of redacted participant consent forms.

19. Are any changes (amendments) requested with this Continuing Review?

Y Yes, please complete the remainder of this form.

No, form is complete. Please submit.

20. Summarize the proposed changes to the protocol in lay terms, including the type of change AND what the change involves.

If this is a change in PI a new Department Chair review is required. Please upload the signed document in the Attachments section.

We would like to increase the sample size from 400 to 750. This change involves using the same protocol on additional subjects by re-instituting the workflow at screening locations. We are also adding a study team member, [name].

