Statistical analysis will be performed using R version 3.3.2 or newer (R Core Team, Vienna, Austria). Binary variables will be created for each sign, symptom, or risk factor based on the corresponding questionnaire response. Standard summary statistics will be calculated for study variables of interest. For continuous variables, statistics included the number of observations (N), mean, standard deviation, and 95% confidence interval. Categorical variables will be summarized in frequency distributions. The results of ABI will be categorized based on the ABI index obtained as normal (>0.9), calcified arteries (>1.4), Mild to moderate disease (0.4-0.9), Severed disease- <0.4 and compared to symptoms (e.g. asymptomatic, claudication, critical limb ischemia). A 'Positive ABI' will then be compared to gold standard 'angiography'; if angiography shows evidence of PAD, this will be termed 'angiographic positive'. Sensitivity will be defined as the proportion of 'ABI positive results' out of the number of samples which were actually 'angiographically positive'. When there are no positive results, sensitivity will not be defined and a value of NA is returned. Similarly, when there are no negative results, specificity will not be defined and a value of NA is returned. Similar statements will be true for predictive values. The positive predictive value will be defined as the percent of predicted positives that are actually positive while the negative predictive value will be defined as the percent of negative positives that are actually negative.

Please save frequently

Protocol Title:

Sensitivity and specificity of digital ankle brachial index (ABI) as a screening tool in detecting peripheral arterial disease: A single center, prospective clinical trial

e) State if deception (including incomplete disclosure of study purpose/procedures) will be used. If so, describe the nature of the deception and provide a rationale for its use. Also, describe debriefing procedures or justify a waiver of the requirement to debrief. NOTE: for studies using deception, an alteration of consent must be justified in the Informed Consent section of the protocol (#13) and the debriefing script/statement must be uploaded in the Attachments section (#16). See IRB Deception Guidelines.

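### Does section 3d need a stated rule for turning right- and left-leg readings into one digital ABI result?

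*Combined protocol and SAP*

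**What the plan says.** Section 3d (data analysis) sets the bands: "The results of ABI will be categorized based on the ABI index obtained as normal (>0.9), calcified arteries (>1.4), Mild to moderate disease (0.4-0.9", and severe disease below 0.4. A positive ABI is then compared with angiography. Sensitivity is the share of positive ABI results "out of the number of samples which were actually" positive on angiography. No sentence in 3d mentions legs.

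Section 1a (Background) says the device "provides bilateral, non-invasive physiologic studies of upper and lower extremity arteries". It also gives the cut-off: "ABI ≤ 0.9 has been used as the criterion for diagnosing PAD". Section 3b, step 6, has the sensor placed in sequence: "Right and left hand fingers and then right and left feet toes". The same step ends: "At the end of 60 seconds, an automated digital ABI will be generated". An interventional radiology physician then files a formal report at the end of the day. Under step 7 the participant either is or is not diagnosed with PAD.

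Item 16 of the continuing review form reports 44 positive results among 238 subjects with usable data: 10 severe, 15 moderate and 19 mild. It attributes the grade to the device.

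**The concern.** A test that reads two legs can give two answers. If the legs fall on opposite sides of 0.9, the participant's band depends on whether the lower leg, the higher leg or an average decides. Section 3d does not choose between them, and its denominator word does not say whether a leg or a person is counted. Sensitivity and specificity are the primary aim, so an unstated rule could move the main result.

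The timing adds to the worry. Items 20 and 21 of the continuing review raise the sample size from 400 to 750 because of a low PPV and a disagreement with the manufacturer's results. A rule settled after that comparison could be suspected of favouring one side. Item 16 also prints PPVs that do not match its own counts, which might suggest that the counting unit had slipped.

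Finally, normal is printed with no ceiling, so read literally a value of 1.5 is both normal and calcified.

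**Working it through.** The plan has no figure of its own to reproduce on this point. Four checks follow.

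**1. Do the bands work?** Taken literally, 0.39 is severe; 0.4 and 0.9 are mild to moderate; 0.905 and 1.4 are normal; 1.41 and 1.5 are both normal and calcified. There is no gap, and the only overlap lies above 1.4. Calcified has its own band starting at 1.4, so normal must end there. The disease bands and the section 1a criterion together put positive at 0.9 or below.

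**2. Is the unit open?** The relevant places agree:
- Section 3b, step 6: one index, in the singular, after all four extremities have been read.
- Section 3d: one index obtained, also in the singular.
- Section 3b, step 7: one PAD call per participant.
- Section 8, items b and c: accrual counted in evaluable subjects.
- Item 16: 10 + 15 + 19 = 44, so each positive subject has exactly one grade.

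Nothing is reported by leg. The word used in 3d for the denominator is loose, but it does not set up a leg-level analysis.

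**3. How much could a leg rule matter if there were two indices?** Legs at 0.85 and 1.05 are mild to moderate by the lower leg, but normal by the higher leg or the mean (0.95). For a wider illustration, take a per-leg false-positive rate p = 0.05. This is the low end of "a specificity of 95% to 100" per cent in section 1a; applying it per leg is an assumption. Treat the 8 + 2 = 10 confirmed subjects as the only cases, leaving 238 − 10 = 228 non-cases. With correlation ρ between legs, P(both) = p² + ρp(1 − p) and P(either) = 2p − P(both).

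| ρ | P(either) × 228 | P(both) × 228 | PPV, either leg: 10/(10 + FP) |
|---|---|---|---|
| 0 | 0.0975 × 228 = 22.2 | 0.0025 × 228 = 0.6 | 31.0% |
| 0.5 | 0.07375 × 228 = 16.8 | 0.02625 × 228 = 6.0 | 37.3% |
| 1 | 0.05 × 228 = 11.4 | 0.05 × 228 = 11.4 | 46.7% |

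For sensitivity in disease of both legs, a per-leg value of 0.83 and independent legs give 1 − 0.17² = 0.971 (either) against 0.83² = 0.689 (both). At ρ = 1 both are 0.83. At 100% per-leg specificity, the top of the quoted range, the rule has no effect on false positives.

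The illustration does not describe this trial. On the same assumption about cases, item 16 implies 44 − 10 = 34 unconfirmed positives and 10/44 = 23% confirmed. No row reaches either figure. The 228 are also not verified non-cases, because step 7 takes no further action after a negative screen.

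**4. Do the item 16 PPVs point to a leg problem?** Item 16 states: "Of the 10 designated severe by QuantaFlo, 8 were confirmed upon follow-up exams and imaging (positive predictive value of 67" per cent. But 8/10 = 80%, and the only whole denominator for which 8/d rounds to 67% is 12. For mild or moderate disease, 2/34 = 5.9%, while the printed 14% fits only 2/14. Counting legs would ordinarily raise 34, not cut it to 14. Follow-up of only some subjects could explain 14 out of 34, but not 12 against 10. The mismatch is real and its cause is not stated, but it is not evidence of a missing leg rule, and writing one would not repair it.

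**The case for a change.** The best case for a change is that 3d really is silent on a matter touching the primary aim, and that a few sentences would settle it. The form's own 3d prompt asks for the smallest reporting unit, and the answer names none. The level at which angiography is judged is not stated, so disease in one leg could in principle be matched to a positive reading in the other. Section 3d also does not say where values above 1.4 go in the accuracy table.

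Much of this stands as description. That the device yields one index per person is an inference from singular wording. The user manual and data sheet are listed as attachments but are not in the documents, so it cannot be confirmed.

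The argument about choosing the rule late is weaker. The physician's report and the participant's PAD call come before any further testing, so a per-participant result exists before the reference result. The plan does not say outright that this report is the analysis variable, and readings could be recoded, but nothing suggests that they would be. For values above 1.4, the printed criterion makes them not positive, since they are not at or below 0.9. The documents report no such values, and no effect is claimed.

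**Conclusion.** No change to the plan is called for. This is an unwritten definition that analysts would fill sensibly, not a stated rule that gives a wrong answer. The natural reading is one index, one category and one reference result per participant, with normal running from above 0.9 to 1.4 and positive meaning 0.9 or below. The open ceiling on normal is a slip of wording.

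No effect on the trial's results is demonstrated. The possible spread (22.2 against 0.6 false positives at one extreme, no difference at the other) rests on assumed per-leg accuracy, assumed correlation and unverified non-cases, and it does not reproduce item 16.

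The conclusion depends on the device or the physician's report giving a single result per participant, as sections 3b and 3d and item 16 indicate. It would need another look if the recorded data turned out to hold two indices per person with no participant-level call. The item 16 percentages that disagree with their counts are a separate reporting matter.

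### Does the overlap between the normal and calcified ABI classes, with no cut-off stated for a positive ABI, leave the accuracy analysis undefined?

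*Combined protocol and SAP*

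**What the plan says.** Section 3d (data analysis) puts the digital ABI into four classes, "normal (>0.9), calcified arteries (>1.4), Mild to moderate disease (0.4-0.9), Severed disease- <0.4", to be summarised and compared with symptoms. The next step moves to accuracy: "A 'Positive ABI' will then be compared to gold standard 'angiography". Sensitivity is then given as follows: "Sensitivity will be defined as the proportion of 'ABI positive results' out of the number of samples which were actually 'angiographically positive". No number and no list of classes is attached to the word positive in that section.

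Four other places bear on the question:

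- The primary aim (Section 2b) depends on the term: "To evaluate the sensitivity and specificity of digital ABI in diagnosing PAD using color Doppler ultrasound and 'gold standard' angiography as reference".
- The background (Section 1a) states that "ABI ≤ 0.9 has been used as the criterion for diagnosing PAD", citing guidelines.
- Item 16 of the continuing review form reports that "QuantaFlo detected positive results for Peripheral Artery Disease in 44 subjects: 10 with severe, 15 with moderate, and 19 with mild disease", out of 238 participants with usable data.
- The clinical course in Section 3b, for participants whose questionnaire and digital ABI do not point to disease, reads "There is no evidence of PAD- no further action will be taken".

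**The concern.** Taken literally, an index of 1.5 is both normal and calcified, so two analysts could place the same participant in different rows of the symptom table, which serves a secondary aim.

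The more serious worry is the primary aim. If positive is not defined, a result above 1.4 could be counted as test-positive, counted as test-negative, or left out. Each choice alters sensitivity when the participant has disease on the reference test, specificity when not, and the predictive values in either case. Accuracy figures have already been seen, and the request to enlarge the study from 400 to 750 cites a low positive predictive value. A rule left open at that point could be chosen to suit the data.

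A further apparent oddity is that Section 1a describes the method as "automated ABI using pulsatile blood volume changes - plethysmography, irrespective of vessel compressibility", while 3d keeps a class named for calcified arteries.

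**Working it through.** **1. How far the overlap extends.** The four classes were applied as written to every index from 0.00 to 2.00 in steps of 0.01, which is 201 values. From 0.00 to 1.40, 141 values each meet exactly one class. From 1.41 to 2.00, 60 values each meet two, normal and calcified. There is no gap or overlap at 0.4 or 0.9. The only fault is the missing upper limit on normal.

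**2. What positive can mean.** The relevant places side by side:

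| Place | What it gives | Consistent with positive = 0.9 or below? |
|---|---|---|
| Section 3d, class labels | Only the classes 0.4-0.9 and below 0.4 are called disease | Yes |
| Section 1a | 0.9 or below as the diagnostic criterion | Yes |
| Continuing review, item 16 | 10 severe + 15 moderate + 19 mild = 44 positives | Yes; 44 - 44 = 0 positives are left for a calcified category |

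None of these treats a value above 1.4 as positive.

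**3. How many participants could be affected.** On this reading, anyone above 1.4 lies among the 238 - 44 = 194 non-positives. The documents do not say how many there are, or whether there are any. Section 3b plans no further action for participants without evidence of disease, so the number of them with a reference test is probably small and may be zero.

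**4. Size if one is verified (illustration only).** Inputs: 8 + 2 = 10 confirmed positives from item 16, taken as true positives; k verified, diseased participants above 1.4; F other false negatives. Both k and F are assumptions.

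- Counted as negative: sensitivity = 10 / (10 + F + k)
- Counted as positive: sensitivity = (10 + k) / (10 + F + k)
- Excluded: sensitivity = 10 / (10 + F)

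| k = 1 | Negative | Positive | Excluded | Positive minus negative |
|---|---|---|---|---|
| F = 0 | 10/11 = 90.9% | 11/11 = 100% | 10/10 = 100% | 9.1 points |
| F = 5 | 10/16 = 62.5% | 11/16 = 68.8% | 10/15 = 66.7% | 6.3 points |
| F = 10 | 10/21 = 47.6% | 11/21 = 52.4% | 10/20 = 50.0% | 4.8 points |

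With k = 0 all three readings agree. Once positive is read as 0.9 or below, the only remaining choice is negative or excluded. Those differ by 9.1, 4.2 and 2.4 points for F = 0, 5 and 10.

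The 10 confirmed cases are a weak base. They rest on follow-up examinations and imaging, whereas 3d defines sensitivity against angiography. The predictive values beside them also do not match their own counts: 8/10 = 80% against a stated 67%, and 2/34 = 5.9% against a stated 14%. The table shows how the calculation behaves and is not an estimate for this trial.

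**The case for a change.** The strongest argument for a change is that positivity is the index-test rule for the primary aim and should be written in the analysis section, not inferred. Section 1a describes guideline practice for ABI in general. The review form separates mild from moderate while 3d combines them, so its grading is not exactly the 3d scheme. Section 3b leaves the PAD call to the questionnaire and the digital ABI, as reported by a physician, without a numeric rule. With interim figures known and few confirmed cases, one reclassification can move sensitivity by several points, and a few lines of text would close the gap.

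Part of this stands. Section 3d is silent, the 0.9 reading is an inference, and it does not settle whether a value above 1.4 is negative or excluded. The rest carries less weight. The mild and moderate split cannot affect positivity, because both grades were counted as positive. The scope for a data-driven choice is narrow: three places point the same way, and the 44 positives have already been reported by grade, so a later switch to counting values above 1.4 as positive would be visible.

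The point about compressibility does not stand. Section 1a describes a measurement principle, and the name of an analysis class does not contradict it.

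The obvious edit, capping normal at 1.4 and defining positive as 0.9 or below, writes down what an analyst would already do. It still would not decide between negative and excluded.

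**Conclusion.** No change to the plan is needed. The missing upper limit on normal is a drafting slip that the separately named class above 1.4 corrects by itself. The missing definition of positive is a gap that an analyst would fill with 0.9 or below, guided by the class labels in 3d and supported by Section 1a and the reported positives. The frequency table by class, already planned in 3d, will show how many results exceed 1.4, so a reader can see whether the point has any bearing.

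The effect has no documented size. It is zero if no participant above 1.4 has a reference test, which the clinical course in Section 3b makes plausible. The 4.8 to 9.1 points per verified, diseased participant rest on 10 true positives and on assumed numbers of other false negatives. The conclusion assumes that results above 1.4 with a reference test are rare. If they proved common, the choice between counting them as negative and excluding them would matter and would have to be reported openly.
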